8.2.2 Subpopulations

Subgroup analyses will be performed on primary, secondary and tertiary efficacy endpoints as defined in section 14. All subgroup analyses will be exploratory and descriptive in nature.

In case of low number of participants within a category (< 25% participants by subgroup categories), subgroup analysis for that variable will not be performed.

Subgroups analyzed are:

1. Subgroup Treatment Course in Cohort B
2. Long-term Responder/Non-responder (4 definitions)
3. Subset Types of Subsequent DMDs
4. Subgroup Prior Use of DMD for cohort B
5. Subgroup HDA for Cohort B

It should be noted that the subgroup analyses on the subgroups' treatment courses and subsequent DMD do not support the comparison of any treatment effect as the definition of subgroups already is not independent from randomized treatment.

1. Subgroup Treatment Course in Cohort B:

- a) **Placebo:** Study participants who received placebo only (i.e. study participants that received placebo in CLARITY who did not enter CLARITY-EXT, or received placebo in both CLARITY and CLARITY-EXT)
- b) **1 treatment course (year) of Cladribine:** Study participants who received at least 1 dose of Cladribine Tablets during either CLARITY or CLARITY -EXT but did not start the 2nd year treatment courses of Cladribine Tablet.
- c) **2 treatment courses (years) of Cladribine:** Study participants who received at least 1 dose of Cladribine Tablets during either CLARITY or CLARITY -EXT that started the 2nd year treatment courses of Cladribine Tablets but did not started a third-year treatment course of Cladribine treatment.
- d) **More than 2 treatment courses (years) of Cladribine:** Study participants who received at least 1 dose of Cladribine Tablets during CLARITY and CLARITY -EXT that started > 2 treatment courses of Cladribine Tablets (i.e. patients who completed CLARITY and started at least the 1st year treatment courses in CLARITY-EXT). This corresponds to participants who completed 2 courses of Cladribine treatment and started the third course of Cladribine treatment.

Computation rules:

The above groups will be determined based on how many treatments years participant had in the parent study:

Year 1: From first Cladribine dose date to End of Year 1.

End of Year 1 is defined as the day of the earliest exposure greater or equal to year 1 start date + 308 days

To define (b), (c) and (d): If at least 1 dose of Cladribine has been administered after end of Year 1, for CLARITY or CLARITY EXT then the participant will be considered starting the second treatment course (year). If at least 1 dose of Cladribine has been administered during the first year of CLARITY EXT after receiving at least 1 dose during the second treatment course of CLARITY, then the participant will be considered starting the third treatment course (year). Individual parent study datasets will be used.

2. Long-term Responder/Non-responder:

a. Primary definition

- **Long-term Responder:** Study participants not requiring DMD 4 years or later following their last dose of IMP, and who did not demonstrate any evidence of disease reactivation based on Investigator assessment of clinical and imaging outcomes
- **Non-Responder:** Study participants requiring DMD less than 4 years following their last dose of IMP or who demonstrate any evidence of disease reactivation based on Investigator assessment of clinical and imaging outcomes.

Computation rules:

Prior/concomitant medication eCRF page and “physician sequential treatment decision questions” eCRF page question 8 and 9 to be used to identify the date of the DMD received.

4 years after last dose of IMP = Last dose of IMP date + 4*365.25 days

Evidence of disease reactivation will be defined by either:

- a) MRI lesions: new T1 lesion or new T2 lesion reported
- b) New Relapse reported
- c) EDSS worsening defined as an EDSS score increase of at least 1 point between 2 consecutive visits of at most 365 days (if 2 consecutive EDSS assessments are separated by more than 365 days then EDSS cannot be used in the criteria and will be considered as missing/not reported).

New relapse, MRI lesions and EDSS worsening will be identified utilizing dates in parent studies for the period between last dose of IMP and end of parent study.

For the period following the end of the parent study until SV1 of Classic study the following source data will be used:

- 1) MRI lesion by the eCRF “frequency stable patient monitoring questions” (fspmq) page,

Q4/Q3. If Q4 is answered “yes” the date will be taken from Q3 and determined if the MRI lesion is before the 4 years since last IMP.

- 2) New relapse will be identified using the eCRF “MS Relapse history” page(hxrelap) Q2.2.
- 3) The EDSS worsening by the eCRF “expanded disability status scale (edssr) for retro data” page.

All partial dates will be imputed as described in Section 9.5.

Different scenarios considering missing/not collected data are provided in the table below:

DMD required	MRI new lesion	New Relapse	EDSS worsening	Responder (Yes/No/ND)
All are missing				ND
At least one is Yes (with or without missing)				No
All are N (with no missing)				Yes
All are N (with at least one missing)				ND

ND=Not determined

b. Definition B (sensitivity):

- **Long-term Responder:** Study participants not requiring DMD 4 years or later following their last dose of IMP.
- **Non-Responder:** Study participants requiring DMD less than 4 years following their last dose of IMP.

c. Definition C (sensitivity)

- **Long-term Responder:** Study participants who did not demonstrate any evidence of disease reactivation based on Investigator assessment of clinical and imaging outcomes 4 years following the last dose of IMP.
- **Non-Responder:** Study participants who demonstrate any evidence of disease reactivation based on Investigator assessment of clinical and imaging outcomes 4 years following the last dose of IMP.

d. Definition D (sensitivity)

- **Long-term Responder:** Study participants who did not demonstrate any evidence of disease reactivation based on Investigator assessment of clinical outcomes 4 years following the last dose of IMP.

- **Non-Responder:** Study participants who demonstrate any evidence of disease reactivation based on Investigator assessment of clinical outcomes 4 years following the last dose of IMP.

Definition A described above is considered the primary definition and will be used in the final analysis. Definition B (definition A revised, using DMD only), Definition C (definition A revised, using reactivation of disease only), and Definition D (as C but removing MRI criteria) will be also performed as a sensitivity analysis. MRI lesions or retro EDSS information are expected to be missing/not collected/not reported. Additional descriptive statistics will be provided for each of the component used in the definition to assess the validity of the criteria.

3. Subset Types of Subsequent DMDs:

- Platform injectable therapy (Interferon- β [Avonex[®], Rebif[®], Betaferon[®], Extavia[®], Plegridy[®]] or glatiramer acetate [Copaxone[®]])
- Monoclonal antibody disease modifying treatment
- Oral disease modifying treatment
- Other subsequent treatment
- Off-label treatments (drugs not approved by regulatory agencies to treat MS)
- No subsequent treatment

Subsequent DMD groups will be identified using a DMD medication lookup list provided by the coding team and reviewed by the medical team. This DMD list will be looked vs all medications reported in prior/concomitant medications, Physician Sequential Treatment Decision eCRF page question 8 in CLASSIC and parent study data. The first subsequent DMD after last dose of IMP will be used to define the subset.

4. Subgroup Prior Use of DMD for cohort B:

- Prior Use of DMD at any time in the patient's history before enrolment into CLARITY
- Complementary subgroup

Prior use of DMD will be identified using same approach described for subsequent DMD using parent study data.

5. Subgroup High Disease Activity for Cohort B:

[figure not shown]
The definition of HDA will be similar to regulatory submission, programs from EMA CSE, will include patients from CLARITY study, and subgroups will be identified using parent study data.

HDA is defined by:

- a) Patients with ≥ 1 relapse during the year prior to parent study entry and ≥ 1 T1 Gd+ lesions or ≥ 9 T2 lesions, while on therapy with other DMDs, OR
- b) Patients with ≥ 2 relapses during the year prior to parent study entry, regardless of prior disease modifying drugs (DMD) use.

Non-HDA is the complementary group.

Table 1: High Disease Activity Definition details

Patients in the previous year while on DMD therapy
	
DMD are medications with preferred term defined in section 12 of the iAP.
 
If more than 1 DMD is used, only last DMD (the closest to Parent Study Day 1 [PSD1]) is considered. Collected start/end date of prior DMD is used to compute prior DMD treatment duration. If end date after PSD1, duration is truncated to PSD1-1. When start/end date are partial (day or month or year missing), imputation rule as described in section 9.5 of the iAP is followed.


Patients should have at least 1 relapse in the previous year while on therapy
	
≥1 relapse in previous year while on therapy. While on therapy is calculated as follows:
 
If duration of DMD treatment is ≥365 days and end date is within 1 year of PSD1, then relapses are considered "while on therapy", if occurring in time period coinciding with DMD therapy.
 
Graphical Representation of Relapse while on therapy
  
Data processing/Handling of partial dates:
 
Relapses with partial onset date are imputed as follows:
 
 • Missing day will be imputed to be 15 and missing month will be imputed to be June. • No imputation for complete missing date. 
Relapses are collected when associated with a date. If no date of relapse is reported, number of relapses is set to 0 (zero).

and have at least 9 T2-lesions
	
≥9 Total T2 lesions prior to first study.
 
Handling of missing data: If T2 lesion is missing prior to first study, subject is considered in the <9 T2 lesions.

or at least 1 Gadolinium-enhancing lesion
	
≥1 T1 Gadolinium-enhancing lesion prior to first study
 
Handling of missing data: If T1 lesion is missing prior to first study, subject is considered in the <1 T1 Gd+ lesion.

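### The SAP's course-counting rule codes two irregular dosing patterns one course lower than its own definitions of courses started

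*SAP*

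**What the plan says.** SAP 8.2.2 (Subgroup Treatment Course in Cohort B) defines four groups: placebo only, one course, two courses, and more than two. The definitions turn on starting a course, as they do in protocol 9.3. The one-course group received cladribine "but did not start the 2nd year treatment courses of Cladribine Tablet". The top group is those "that started > 2 treatment courses of Cladribine Tablets", explained as "patients who completed CLARITY and started at least the 1st year treatment courses in CLARITY-EXT", with a further gloss: "This corresponds to participants who completed 2 courses of Cladribine treatment and started the third course of Cladribine treatment".

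The computation rules then give the dates. They set "Year 1: From first Cladribine dose date to End of Year 1", and "End of Year 1 is defined as the day of the earliest exposure greater or equal to year 1 start date + 308 days". The condition for a second course begins "If at least 1 dose of Cladribine has been administered after end of Year 1, for CLARITY or CLARITY EXT". The only condition for a third course is a dose "during the first year of CLARITY EXT after receiving at least 1 dose during the second treatment course of CLARITY". The paragraph ends by saying that the individual parent study datasets are used. It does not say whether End of Year 1 is set once for a patient or separately in each study.

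The grouping appears in the demographics (SAP 11.1) and in two listed efficacy tables, 15.2.1.2.2 and 15.2.2.2.2 (SAP 17.1).

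**The concern.** The rule should reproduce the definitions, and in two places it is narrower. The boundary that closes Year 1 is itself the dose that opens Year 2, so that dose is not counted towards Year 2. The third-course condition names one path through the two trials, although other paths can also give three started treatment years.

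In both places the result is a lower count than the definitions give. The patients concerned are those who stopped or interrupted dosing, and they may differ in prognosis from patients dosed on schedule. They would be described in the wrong stratum. Two programmers could also code the rule differently.

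**Working it through.** The plan gives no figure to reproduce, so the check is to apply the rule literally to dosing histories and compare the result with the number of treatment years started.

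**Inputs**
- Threshold: 308 days after the first cladribine dose, 308 / 7 = 44 weeks (SAP 8.2.2).
- Last scheduled Year 1 dosing: Week 13, over at most 5 days (SAP 6.2). Offset: (13 − 1) × 7 + (5 − 1) = 88 days.
- First scheduled Year 2 dosing: CLARITY lasted 96 weeks over two years (SAP 6.2). With equal years (an assumption), 96 / 2 × 7 = 336 days; with 52-week years, 52 × 7 = 364 days.
- Gap from CLARITY to CLARITY-EXT: 1 day to 118 weeks, median 41 weeks (SAP 6.2), so 1, 287 and 826 days were tried.

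**Step 1, the boundary.** 88 < 308 < 336 (or 364). On schedule, no Year 1 dose reaches day 308, so the first exposure at or beyond it is the first Year 2 dosing day. Call that day E.

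**Step 2, second course.** The rule needs a dosing day later than E. With a single Year 2 dosing day, that day equals E, and E > E is false: 1 course. With a second dosing day, E + 1 > E is true: 2 courses.

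**Step 3, third course.** The rule needs a dose in the second CLARITY course and then one in CLARITY-EXT Year 1. Without CLARITY Year 2 dosing, the first condition fails whatever happened in the extension.

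**Results**, with one End of Year 1 per patient (the same for both year lengths and all three gaps):

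| Cladribine dosing | Courses started | Rule gives |
|---|---|---|
| CLARITY Y1 and Y2 in full | 2 | 2 |
| CLARITY Y1, one treatment week of Y2 | 2 | 2 |
| All four years in full | >2 | >2 |
| CLARITY Y1, one day of Y2 | 2 | **1** |
| Placebo in CLARITY; EXT Y1, one day of EXT Y2 | 2 | **1** |
| CLARITY Y1, EXT Y1, EXT Y2 | >2 | **2** |

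Regular histories are coded correctly. Each failing row is exactly one course too low. The first fault has a knock-on: CLARITY Y1, one day of Y2, then EXT Y1 is coded 2 instead of >2 if the second CLARITY course is taken to begin after End of Year 1.

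**Dataset scope.** CLARITY Y1 plus EXT Y1 is coded 2 with a single End of Year 1. It is coded 1 if the boundary is set within each study, because neither study alone then shows a second year. The text permits both readings.

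**Effect of the repair.** Replacing after by on or after moves the single-day rows from 1 to 2. It leaves CLARITY Y1 + EXT Y1 + EXT Y2 at 2. Counting treatment years with at least one dose corrects that row as well.

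**The case against.** The strongest reply is that this hardly matters. The first fault reaches only patients with exactly one dosing day at or beyond day 308, when a treatment week runs 4 to 5 days. The second needs a patient who had no cladribine in CLARITY Year 2, still completed CLARITY, and then took both extension years. The documents report no such patients. SAP 8.2.2 and 14 also drop a subgroup analysis when a category holds under 25% of participants. Four shares that sum to 100% can all reach 25% only if each is exactly 25%, so the efficacy tables would almost certainly not be produced. The SAP adds that this subgroup cannot support a treatment comparison. All of this stands and limits the size of the point. It does not remove the conflict between rule and definition: SAP 6.2 describes extension entry as completing the CLARITY study, without stating that Year 2 dosing was required.

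A reader might infer more than the text supports in four ways:
- **Group (d) loses patients who did not complete a second course.** It does not. The computation rule asks only for at least one dose in the second CLARITY course, so such a patient who then doses in CLARITY-EXT Year 1 is placed in (d). The word completed sits in a gloss.
- **Both CLARITY years plus only the second extension year is miscoded.** This depends on whether the first extension year is read by calendar or from the first extension dose. On the calendar reading, the patient also fails the explanation in (d).
- **Everyone who took only the first Year 2 week is miscoded.** That would need weekly exposure records compared by start date. The documents give no record structure, and the rule counts doses, with one dose defined as one tablet.
- **The wheelchair or EDSS results by course are materially shifted.** Those tables are the ones that the 25% rule would suppress.

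**Conclusion.** The point holds in a narrow form. Read literally, the rule contradicts the definitions it implements in two irregular dosing patterns, each one course too low: a single dosing day at or beyond day 308, and CLARITY Year 1 followed by both extension years. The one-course size of the error assumes a single End of Year 1 per patient; a boundary set per study adds further undercounts.

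The number of patients cannot be derived from the documents and is probably small. The visible effect is mainly in the descriptive treatment-course row of the demographics. This assumes that the 25% is taken over the cohort's participants and that all four categories are kept. The exposed/never-exposed grouping (SAP 8.2.1) needs only one cladribine dose and is unaffected. This is a clarification worth making, not a threat to the main results.

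**What to change.** In SAP 8.2.2:
1. Change after to on or after End of Year 1, so that Year 2 starts on the first dose at or beyond day 308.
2. Assign 1, 2 or more than 2 courses by counting the treatment years across CLARITY and CLARITY-EXT in which the patient had at least one cladribine dose.
3. State whether End of Year 1 is set once or per parent study. If per study, say that the years are added across studies.
4. Align the gloss about completing two courses, in SAP group (d) and in protocol 9.3, with the word started. This is wording only, and both documents should change together because SAP section 7 declares no departures from the protocol.

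The cost is a few lines of text and a simpler derivation on data already held. One consequence should be noted: the Cohort B demographics table is marked as an interim output (SAP 17.1), and SAP 6.4 says that interim results have been disseminated. The treatment-course row may therefore differ from the interim version, and a footnote should explain any change.

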Subset Long-term Responder	Study participants 
 • not requiring DMD until Year 4 or later following their last dose^a of IMP, and who did not demonstrate any evidence of disease reactivation based on Investigator assessment of clinical and imaging outcomes • who started on alternate therapy (DMD) less than 4 years following their last dose^a of IMP or who demonstrate any evidence of disease reactivation based on Investigator assessment of clinical and imaging outcomes.
Subset Types of Subsequent DMDs	
 • Platform injectable therapy (Interferon-β [Avonex[®], Rebif[®], Betaferon[®], Extavia[®], Plegridy[®]] or glatiramer acetate [Copaxone[®]]) • Monoclonal antibody disease modifying treatment • Oral disease modifying treatment • Other subsequent treatment • Off-label treatments (drugs not approved by regulatory agencies to treat MS) • No subsequent treatment
Subgroup Prior Use of DMD	
 • Prior use of DMD at any time in the patient's history before enrolment into CLARITY • Complementary subgroup
Subgroup HDA for Cohort B	
 • HDA study participants • Non-HDA study participants

DMD=disease-modifying drug, HDA=high disease activity, MS=multiple sclerosis.

^a One dose is equivalent to one tablet. One course of IMP is defined as 1 year of treatment with IMP (2 treatment cycles [weeks]. A treatment cycle is defined as daily administration of IMP given consecutively over 4-5 days during a 28-day period. One treatment week is equivalent to 1 treatment cycle.

The primary and selected secondary or tertiary analyses may be repeated by these subgroups/subsets in order to evaluate the pattern of response.

It should be noted that the subgroup analyses on the subgroups' treatment courses and subsequent DMD do not support the comparison of any treatment effect as the definition of subgroups already is not independent from randomized treatment.

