To evaluate long-term mobility after treatment with an investigational medicinal product (IMP; Cladribine Tablets or placebo) as part of the Phase III ORACLE MS and CLARITY/CLARITY-EXT clinical trials.	Proportion of study participants using a wheelchair (defined as unable to walk beyond approximately 5 meters even with aid, essentially restricted to wheelchair; wheels self in standard wheelchair and transfers alone; up and about in wheelchair some 12 hours a day) the majority of the time in the 3 months prior to Study Visit 1 (SV1) or participants are bedridden any time prior to SV1, determined via: 1) Expanded Disability Status Scale (EDSS) score of 7.0 or higher), or Alternative clinical description data in medical records.	Section 14.1
Secondary		

Objectives	Endpoints (Outcome Measures)	IAP section
To assess the long-term disability status after treatment with IMP as part of the Phase III ORACLE MS and CLARITY/CLARITY-EXT clinical trials for the CLARITY/CLARITY-EXT and ORACLE MS populations.	Proportion of study participants with EDSS of 6.0 or higher as determined by EDSS documentation or alternative clinical description in medical records after last IMP from parent study.	Section 14.2.1
To evaluate differences in clinical characteristics between long-term responders and study participants requiring alternate therapies following treatment with IMP for the CLARITY/CLARITY-EXT and ORACLE MS populations.	Clinical characteristics ^a at Study Visit 1 of long-term responders (defined as study participants who did not demonstrate any evidence of disease reactivation based on Investigator assessment of clinical and imaging outcomes until Year 4 or later following their last dose ^b of IMP and who did not receive disease modifying treatment until Year 4 or later following their last dose ^b of IMP) compared to those of other study participants who started on alternate therapy less than 4 years following their last dose ^b of IMP for the CLARITY/CLARITY-EXT and ORACLE MS populations.	Section 14.2.2

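### The SAP's primary long-term-responder rule puts no 4-year limit on relapse or EDSS worsening, although the endpoint does

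*SAP*

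**What the plan says.** **Endpoint.** Protocol 1.1 and 3 and SAP 5 describe long-term responders as participants who "did not demonstrate any evidence of disease reactivation based on Investigator assessment of clinical and imaging outcomes until Year 4 or later" after their last IMP dose, and who also took no DMD before that time. Both conditions carry the same limit. The endpoint compares them with participants who started alternate therapy less than 4 years after the last dose.

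**Definition A.** SAP 8.2.2 classes as non-responders "Study participants requiring DMD less than 4 years following their last dose of IMP or who demonstrate any evidence of disease reactivation". The limit sits on the DMD limb only. Protocol 9.3 has the same shape: its second group is bounded by 4 years for DMD and then continues "of IMP or who demonstrate any evidence of disease reactivation based on Investigator assessment of clinical and imaging outcomes", with no limit.

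**Computation rules (SAP 8.2.2).** The 4-year date is given as last IMP dose plus 4 × 365.25 days. Parent-study dates cover the time up to the end of the parent study. After that: "For the period following the end of the parent study until SV1 of Classic study the following source data will be used". For MRI lesions, "the date will be taken from Q3 and determined if the MRI lesion is before the 4 years since last IMP". For relapse and EDSS worsening only the eCRF page is named. EDSS has a further rule: "if 2 consecutive EDSS assessments are separated by more than 365 days then EDSS cannot be used in the criteria". In the decision table, one positive component is enough for non-response.

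**Other definitions.** Definition C, described as a revision of A using reactivation only, refers to "assessment of clinical and imaging outcomes 4 years following the last dose of IMP"; Definition D has similar timing. However, "Definition A described above is considered the primary definition and will be used in the final analysis".

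**The concern.** The rule that will be programmed is stricter than the endpoint, and strict on only two of its four components. A participant who was relapse-free and untreated for 4 years meets the endpoint whatever happens later. Under Definition A as written, a first relapse or EDSS worsening at any time up to Study Visit 1 removes that status.

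Responder status forms the groups for clinical characteristics (SAP 14.2.2) and MRI characteristics (14.2.3). It is also the rate compared between HDA and non-HDA patients (14.3.5) and the outcome in the genetic association (14.3.6). Participants with late events would leave the responder group and join the group it is compared with. SAP 7 declares no change from the protocol, so nothing signals a deliberate departure from the endpoint.

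**Working it through.** The plan gives no figure to reproduce, so the check compares two rules and then sizes the exposed period.

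**1. Rule comparison.** Rule S is SAP 8.2.2 as written: 4-year limit on DMD and MRI, none on relapse or EDSS worsening. Rule E is the endpoint: 4-year limit on all four. In both, any positive component means non-responder. Times are years after the last IMP dose.

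| Only event | Rule S: responder? | Rule E: responder? |
|---|---|---|
| None | Yes | Yes |
| Relapse at 3 | No | No |
| Relapse at 5 | **No** | **Yes** |
| EDSS worsening at 6 | **No** | **Yes** |
| MRI lesion at 5 | Yes | Yes |
| DMD start at 5 | Yes | Yes |

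The rules differ in two of six cases, both in the same direction. Rule S counts every event that Rule E counts plus the later ones, so with complete data it can only lose responders. Applying the 4-year date (1,461 days) to relapse and EDSS makes the rules agree in all six.

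**2. Share of the searched period after year 4.** Inputs: visits around 10 years after first treatment (Protocol 9); 96-week parent studies dosed in weeks 1 and 5 of each year, and a CLARITY to CLARITY-EXT gap with median 41 weeks, range 1 day to 118 weeks (SAP 6.2); ORACLE MS dosing stopped in October 2011 (SAP 6.2); enrolment from about Q3 2019 (Protocol 4.1). Assumed: full dosing and 48-week study years, so the last dose falls at about week 48 + 5 = 53 of each 96-week study.

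Share = (T − 4)/T, where T is years from last dose to Study Visit 1.

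- CLARITY only: 53 weeks = 1.02 years; T = 10 − 1.02 = 8.98; share = 4.98/8.98 = 55%.
- CLARITY-EXT, median gap: 96 + 41 + 53 = 190 weeks = 3.64 years; T = 6.36; share = 2.36/6.36 = 37%. A 1-day gap gives T = 7.14 and 3.14/7.14 = 44%; a 118-week gap gives T = 4.88 and 0.88/4.88 = 18%.
- ORACLE MS: 31 October 2011 to 1 July 2019 gives T of at least 7.67; share at least 3.67/7.67 = 48%.

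Stopping IMP early lengthens T and raises the share. These are shares of calendar time, not of events.

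**3. Why the number reclassified stays open.** The documents give no relapse rate after year 4. As illustration only, assume a constant rate r and w years between year 4 and Study Visit 1; the chance of a relapse in that time is 1 − exp(−r·w). At r = 0.03 and w = 2 it is 5.8%; at r = 0.14 (the 2-year cladribine rate quoted in Protocol 2.2) and w = 5 it is 50.3%. The form of the model matters too. At a rate of 0.10 and T = 9, a constant rate gives 1 − exp(−0.5) = 39.3%. Gamma-distributed risk with assumed shape 0.5 gives 1 − (2.8/1.8)^(−0.5) = 19.8% among those relapse-free at year 4. The range is too wide to serve as an estimate.

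**The case against.** The strongest reply is that the intent is clear from context. SAP 5 states the limit, the 4-year date heads the computation rules, Definitions C and D mention 4 years, and partial event dates are to be imputed, which suggests that they are used. Definition A's responder limb also has an obvious slip about DMD (not required at or after 4 years) that any reader corrects from its paired line. This stands as evidence of a drafting omission. It does not close the gap: no text applies the date to relapse or EDSS worsening in Definition A, and stating the check for MRI alone invites programming the other two without it.

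Second, SAP 8.2.2 follows Protocol 9.3. That is correct, and it means the protocol conflicts with its own section 3. Correcting the SAP alone would leave it at odds with Protocol 9.3.

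Third, the study is exploratory and the SAP has sensitivity definitions and component summaries. This limits the severity. But Definition B uses DMD only, C reactivation only and D clinical reactivation only, so none reproduces the two-part endpoint. Appendix 17.1 lists the HDA responder-rate table once, with no sensitivity version.

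A reader might also infer that missing data fall mainly on true responders, because one event settles non-response while response needs all four components observed. Per person, responders are indeed more easily left undetermined. In numbers, the result depends on a responder rate that the documents do not give. Suppose MRI and EDSS are each observed with probability 0.8, and non-responders' only event lies in one of them. True responders are then 0.5 × 0.36/(0.5 × 0.36 + 0.5 × 0.2) = 64% of the undetermined at a true rate of 50%, but 0.25 × 0.36/(0.25 × 0.36 + 0.75 × 0.2) = 37.5% at 25%. A claim that the SAP's 25% subgroup threshold would flip with the choice of denominator likewise holds only for selected values. Neither is a demonstrated fault of the plan.

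**Conclusion.** The inconsistency is established from the text. As written, Definition A reclassifies endpoint-defined responders whose first relapse or EDSS worsening comes after year 4, and the effect runs one way. Between 37% (CLARITY-EXT at the median gap) and 55% (CLARITY only) of the period searched lies after the limit, taking visits at about 10 years and full dosing. The number of participants affected cannot be derived.

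A reader might infer that the study's main result is compromised. The documents do not support that: the overall primary-endpoint estimate does not use responder status, and only its breakdowns by responder subset do. The affected secondary and tertiary analyses are descriptive and hypothesis-generating. Nor do the documents show which rule was actually programmed. The point should be fixed before the final analysis.

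**What to change.** In SAP 8.2.2:

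- Apply one window, last IMP dose to last IMP dose plus 4 × 365.25 days, to DMD, relapse, EDSS worsening and MRI lesions in Definition A.
- Apply the same window to the 365-day EDSS-gap rule, so that a gap after year 4 cannot leave a participant undetermined.
- Correct the DMD phrase in the responder limb of Definitions A and B so that it means no DMD before year 4.

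Reconcile Protocol 9.3 with Protocol 3 at the same time. Also reconcile the SAP non-responder group, which includes reactivation without DMD, with the endpoint's comparator of participants who started alternate therapy within 4 years; the time window alone does not resolve that difference.

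Record the change in the SAP modification history. Table 15.2.3.1.1 (Cohort A responders) is marked for the interim analysis, whose results SAP 6.4 says have been disseminated, so the report should note that it may have used the rule without the limit. Showing undetermined participants in their own row is an optional reporting aid.

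The cost is small. The cut-off is already defined, relapse onset dates are collected where available (Protocol 8.1.1.7), and the EDSS rule already relies on visit dates, so no new data are needed. The downside is that final responder figures may not be comparable with the interim ones.
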